7.2.2 Supplementary Analysis

A mixed model of repeated measures (MMRM) model will be used as supplementary analyses to analyse the change from baseline in FVC using the same fixed effects, for treatment, randomization stratum (background therapy), age, and baseline FVC along with treatment-by-time interaction and background therapy status-by-time interaction, as in the random coefficients linear regression model. MMRM assume a nonlinear decline in lung function over time. An unstructured variance covariance structure, same as used in the primary analysis, will be used to model the within-patient measurements variability. If the unstructured covariance structure matrix results in a lack of convergence, first-order autoregressive, AR(1), covariance structure will be used. The Kenward-Roger approximation will be used to estimate the denominator degrees of freedom.

The comparison will be conducted to evaluate the treatment difference in absolute FVC at week 26 and 38 between BG0011 cohort versus placebo cohort, respectively.

- If a subject who experiences unscheduled visit(s) for acute exacerbation of IPF and has non-missing FVC measurement(s), such unscheduled FVC measurement(s) may be included in the analysis by using the follow rule.
- If the unscheduled FVC measurement is between 2 consecutives post-baseline scheduled visits with both FVC measurements non-missing, the unscheduled FVC measurement(s) will not be included in the model. If more than one unscheduled FVC measurements are between the same visit window (between the same 2 consecutives post-baseline scheduled visits), all unscheduled FVC measurements will not be included in the model.
- If the unscheduled FVC measurement is between 2 consecutives post-baseline scheduled visits with one of the two FVC measurements missing, the unscheduled FVC measurement will be included in the model and imputed as the schedule visit with missing FVC value. If more than one unscheduled FVC measurements are between the same visit window, the unscheduled FVC measurement which is closest to the scheduled visit with missing FVC measurement will be included in the model and imputed as the schedule visit with missing FVC value.
- If the unscheduled FVC measurement is between 2 consecutives post-baseline scheduled visits with FVC measurements missing at both visits, the unscheduled FVC measurement will be included in the model and imputed to the scheduled visit which is closer to the unscheduled visit. If the unscheduled visit is in the middle of the 2 schedule visits, the unscheduled FVC measurement will be included in the model and imputed to the earlier scheduled visit. If more than one unscheduled FVC measurements are between the same visit window, the earliest unscheduled FVC measurement and the latest unscheduled FVC in the same visit window will be included in the model and the earliest unscheduled FVC measurement will be imputed to the earlier scheduled visit and the latest unscheduled FVC measurement will be imputed to the later scheduled visit.

Since the study stops early, Table 1 will be applied to define the visit window for FVC measurement at the early termination visit.

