6.1.1.4 Early Termination or Unscheduled Visits for Acute Exacerbation of IPF

In general, when data are summarized by analysis visit, the Early Termination Visit or Unscheduled Visits for Acute Exacerbation of IPF will be assigned to an appropriate scheduled analysis visit by using a window scheme provided in Table 1.

Table 1: Visit Windows for Early Termination or Unscheduled Visits

Scheduled Visit Time	Target study day	Analysis visit window (days)	
		Efficacy & Safety Data	PK Data
Baseline (Day 0)	1	Most recent non-missing value on/before the date of first dose	
Day 5*	6	N/A	[6,7]
Week 4	29	[2,43]	[8,43]
Week 8	57	[44,71]	
Week 12	85	[72,99]	
Week 16	113	[100,127]	
Week 20	141	[128,162]	
Week 26	183	[163,203]	
Week 32	225	[204,246]	
Week 38	267	[247,288]	
Week 44	309	[289,337]	
Week 52	365	[338,393]	
Safety Follow-up (Week 60)	421	
 • If subject who discontinued treatment due to reasons other than study termination by sponsor: > min (393, study day of each subject's week 52/EOT visit in treatment period) ** • If subject who discontinued treatment due to study early termination by sponsor: > min (393, study day of each subject's last dose) 	

*The Day 5 Visit is for blood collection only (for PK analysis) and may be done in the clinic or at home (by appropriate personnel). Sample collection should occur on Day 5 (not sooner), with a +1 day window allowed (i.e., collection should occur on Day 5 but may occur on Day 6).

** For subjects who discontinued the treatment due to reasons other than study termination by sponsor will go on to complete all scheduled visits until either week 52 or the study was terminated by sponsor due to the urgent safety measure whichever occurs first. The Week 52/ EOT visit in treatment period is defined as the last visit scheduled for either week 52 or study termination due to the urgent safety measure.

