The lower bound and the upper bound for the visit windows are defined as the midpoints of the scheduled visits. If the date and time from early termination visit or unscheduled visit for acute exacerbation falls in between the lower bound and the upper bound for a scheduled visit, then it will be assigned to that visit. If there are 2 or more assessments available in the same analysis window for a subject, the assessment that is closest to the target visit day will be used for analysis. If there are 2 or more assessments in the same analysis window with the same distance from the target visit day, the earlier/earliest assessment will be used.

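### In the supplementary MMRM, exacerbation FVCs can fill a missing scheduled visit regardless of distance, so Weeks 26 and 38 can take values from well outside their Table 1 windows

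*SAP*

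**What the plan says.** SAP 6.1.1.4 gives the general rule. Early termination and exacerbation visits "will be assigned to an appropriate scheduled analysis visit by using a window scheme provided in Table 1". On the windows it says "The lower bound and the upper bound for the visit windows are defined as the midpoints of the scheduled visits", and when several assessments fall in one window, "the assessment that is closest to the target visit day will be used for analysis".

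SAP 7.2.2 then sets its own rules for exacerbation FVCs in the MMRM:

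- Both neighbouring scheduled FVCs observed: the exacerbation value is not used.
- Exactly one neighbour without an FVC: the rule reads "the unscheduled FVC measurement will be included in the model and imputed as the schedule visit with missing FVC value". With several values in the gap, the one closest to the missing visit is taken.
- Both missing, one value: it is "imputed to the scheduled visit which is closer to the unscheduled visit".
- Both missing, several values: the earliest goes to the earlier visit, and "the latest unscheduled FVC measurement will be imputed to the later scheduled visit".

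The section brings in Table 1 for one purpose only: "Table 1 will be applied to define the visit window for FVC measurement at the early termination visit". It does not say whether 6.1.1.4 or 7.2.2 governs exacerbation FVCs. The specific rule displaces the general one by implication.

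**The concern.** The MMRM contrasts are read at Weeks 26 and 38, and the model treats every value filed under a visit as measured at that visit. A rule that ignores distance can label a measurement with a time point about six weeks away, although an observed scheduled value may lie one day from it. The MMRM is also the check on the linear-decline assumption of the primary model, which uses continuous time. If the same measurement carries different times in the two models, a disagreement between them may reflect relabelled dates rather than non-linearity. SAP 7.3.1.1 applies the same supplementary analysis to percent predicted FVC.

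**Working it through.** **Inputs.** SAP Table 1 target days: Week 20 = 141, Week 26 = 183, Week 32 = 225, Week 38 = 267, Week 44 = 309. Table 1 windows: Week 20 [128,162], Week 26 [163,203], Week 32 [204,246], Week 38 [247,288], Week 44 [289,337]. Assumed declines from SAP section 4: 110 mL/year on background therapy and 220 mL/year without; planned effect 82.5 mL/year.

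**Reproducing the Week 26 window.** (141 + 183)/2 = 162 and (183 + 225)/2 = 204. The lower bound of 163 follows. The midpoint day 204 is given to Week 32, so the upper bound is 203. At the other boundaries the midpoint day goes to the earlier visit, so this is only a one-day tie placement.

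**One neighbour missing.** Suppose the named visit is missing and both its neighbours were observed on target.

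| Missing visit | Days mapped by 7.2.2 | Table 1 window | Mapped days outside the window |
|---|---|---|---|
| Week 26 | 142-224 (82 days without day 183) | 163-203 | 142-162 and 204-224: 21 + 21 = 42 (51%) |
| Week 38 | 226-308 (82 days without day 267) | 247-288 | 226-246 and 289-308: 21 + 20 = 41 (50%) |

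Largest distance from target: 183 - 142 = 41 days, and the same for 224 - 183, 267 - 226 and 308 - 267. A day-142 value is one day after the observed Week 20 test, yet is analysed as Week 26. Under Table 1 it belongs to Week 20, where the day-141 value is closer to target, so Week 26 stays missing. The limits move with actual visit days. At the edges of the protocol windows (Week 20 ±3, Week 32 ±7) the Week 26 range could be 141 - 3 + 1 = 139 to 225 + 7 - 1 = 231.

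**Both neighbours missing, several values.** With Weeks 20 and 26 missing and exacerbation FVCs on days 142 and 143, the first becomes Week 20 and the second Week 26, which is 183 - 143 = 40 days from target. Table 1 places both in Week 20.

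**Collisions.** With Weeks 20 and 32 observed, exacerbation values on days 150 and 215 both map to a missing Week 26. The tie-break covers only values within one gap. An early-termination FVC on day 165 (Week 26 by Table 1) can likewise meet an exacerbation FVC on day 150 (Week 26 by 7.2.2, if the unattended visit counts as missing). No precedence is given, and the model needs one value per subject and visit.

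**Size of the timing error.** Per affected subject at 41 days: 110 × 41/365 = 12.4 mL; 220 × 41/365 = 24.7 mL. This leaves out any FVC drop from the exacerbation itself.

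Group level, assuming a share of 2% to 10% of an arm, all at the 41-day extreme: 0.02 × 12.4 = 0.25 mL to 0.10 × 24.7 = 2.5 mL. For scale, the planned effect at Week 26 is about 82.5/2 = 41 mL.

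**After restriction to Table 1.** The largest distance falls to 183 - 163 = 20 days at Week 26 and 288 - 267 = 21 days at Week 38.

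**The case against.** The strongest reply is that 6.1.1.4 states only a general rule, so 7.2.2 may set a prespecified exception for one model. That model is supplementary, and SAP 6.7 makes all inference nominal. The values at issue come from subjects who exacerbated and then missed a visit, so their missingness may be informative. An off-target observation could be better than a prediction under MAR. Timing errors also run both ways: early values understate decline and late ones overstate it.

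All of this limits the size, and the trade-off with MAR is real. It does not justify the rule. A value taken one day after an observed Week 20 test says little about Week 26, and 7.2.2 itself uses closeness when both neighbours are missing and there is a single value.

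The reply also shows that simply deleting the 7.2.2 rules would be wrong. Take a scheduled Week 26 FVC on day 186 (3 days from target) and an exacerbation FVC on day 184 (1 day from target). The closest-to-target rule in 6.1.1.4 would then replace the scheduled value with the exacerbation value. With the neighbouring scheduled FVCs observed, 7.2.2 prevents this.

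**Conclusion.** The rule mistimes data at the two visits the MMRM reports and should be corrected. The error is up to 41 days with neighbours on target, or 12-25 mL per affected subject at the SAP's assumed declines. The group-level shift is probably small and depends on a share affected that the documents do not give.

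A reader might infer more, but the documents do not support it:

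- *That any distance is possible.* The adjacent scheduled visits bound it, and a single value with both neighbours missing already goes to the closer visit.
- *That 25 mL is comparable with the 41 mL effect.* The first is an extreme for one record; the second is a difference in group means.
- *That the primary result is biased.* The primary and complementary models treat time as continuous and are not affected.
- *That Week 52 is distorted.* A day-310 value could be filed there, but it is not a reported contrast.
- *That a transient dip is carried forward, more often in one arm.* The documents give neither the course of FVC after an exacerbation nor rates by arm. Protocol 4.1 describes a poor prognosis afterwards.
- *That DLco and TLC are affected.* SAP 7.3.1.1 borrows the 7.2.2 model for them, but the assignment rules are worded for FVC only, and carry-over is not stated.

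**What to change.** Revise SAP 7.2.2 as follows.

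1. Keep the priority of an observed scheduled FVC: an exacerbation value never replaces it.
2. Where the scheduled FVC is missing, use an exacerbation FVC only if it falls in that visit's Table 1 window. Among exacerbation and early-termination values in the window, take the one closest to the target day. This also settles the collisions.
3. If no value falls in the window, leave the visit missing.
4. State that this overrides the other mapping rules for the MMRM, including the closest-to-target choice in 6.1.1.4 where it would displace a scheduled value.
5. State whether the rule applies to DLco and TLC.

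The cost is a few sentences, somewhat simpler programming, and a few more missing visit values handled under MAR. Those values would no longer count toward the 20-subject minimum at Weeks 26 and 38. SAP 1.1 allows documented revisions.

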7.2.3 Complementary Analysis

The estimand of this complementary analysis is the mean difference of the change from baseline in FVC (expressed in mL over 52 weeks, i.e. mL/year) between treatment and placebo group in the MITT. All observed on-treatment and the retrieved dropout data including those collected after experienced intercurrent event (i.e. death and/or lung transplantation and/or treatment discontinuation) and prematurely discontinue the study treatment will be applied as observed, no imputation will be implemented [[ICH E9 \(R1\) Addendum 2017](#)]. The estimate of this analysis reflects the treatment effect of BG00011 seen as actually taken [*de facto* effectiveness estimand]. All data after intercurrent events are included, the same random coefficients linear regression model described in [Section 7.2.1](#) will be applied. In this complementary analysis, missing data are assumed to be missing at random [[Rubin 1976](#)] and no imputation will be applied.

Similar to the primary analysis, the complementary analysis will be evaluated at week 26 and week 38, respectively.

7.3 Analysis of Secondary Efficacy Endpoints

7.3.1 Analysis of Continuous Endpoints

7.3.1.1 Pulmonary Function Tests

The continuous secondary efficacy endpoint of change from baseline in percent predicted FVC, at week 26 and week 38 will be applied using the primary analysis, supplementary analysis and complementary analysis described in [Section 7.2](#).

The continuous secondary efficacy endpoints listed as follows will be applied using MMRM model described in [Section 7.2.2](#). Similarly, if less than 20 subjects (i.e. <20 subjects) had non-missing measurements for any endpoint at a given visit time of interest, the mean difference comparison will not be performed at that visit time for that endpoint due to the insufficient data.

- Change from baseline in DL_{co}, corrected for hemoglobin (DL_{co}/Hb) at weeks 26 and 38, respectively.
- Change from baseline in percent (%) predicted DL_{co}/Hb at weeks 26 and 38, respectively.
- Change from baseline in TLC at weeks 26
- Change from baseline in percent (%) predicted TLC at weeks 26

Because the study stopped early, the following continuous secondary efficacy endpoints could not be evaluated with insufficient data.

- Changes from baseline in percent (%) predicted FVC over 52 weeks
- Changes from baseline in DL_{co}/Hb absolute over 52 weeks.
- Changes from baseline in percent (%) predict DL_{co}/Hb over 52 weeks.
- Changes from baseline in total lung capacity (TLC), as measured by plethysmography, over 52 weeks.

- Changes from baseline in percent (%) predicted TLC over 52 weeks.

All the continuous secondary endpoints listed below will be summarized by descriptive statistics at each scheduled visit time. The measurement and change from baseline will be presented. Plots of mean value with standard error for each of the following continuous secondary endpoints at each visit will also be presented.

- FVC
- Percent (%) predicted FVC
- DL_{co}/Hb
- Percent (%) predicted DL_{co}/Hb
- Total lung capacity (TLC), as measured by plethysmography
- Percent (%) predicted TLC

7.3.1.2 6-Minute Walk Test (6MWT)

6MWT distance and change from baseline in 6MWT distance will be summarized and presented by descriptive statistics at each scheduled visit time.

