13.1.1.2. Carbon Monoxide Diffusion Capacity

DL_{CO} measurement will be performed at Screening to determine study eligibility, and at the following study visits: Baseline (Day 0), Week 4, Week 8, Week 16, Week 26, Week 38, and Week 52.

Evaluation of DL_{CO} will be performed by single-breath carbon monoxide diffusing capacity according to ATS/ERS recommendations. See the Study Reference Guide for full details of the DL_{CO} testing procedure.

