2. A mixed model of repeated measures model will be used to compare the difference between the 2 treatment groups in FVC change at 52 weeks and other scheduled visits. An unstructured variance-covariance structure will be used in this model. If the model fails to converge, an AR(1) structure will be used.
3. Rate of decline in percent predicted FVC at 52 weeks will be analyzed by the same method as FVC actual value.

A model including the interaction between treatment and background therapy strata will be used to explore the treatment effects within each subgroup.

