16.2.2.3. Analysis of the Secondary Endpoints

Time to progression will be presented using Kaplan-Meier curves, a stratified log-rank test will be used to compare the 2 treatment groups using randomization stratum as the stratification factor. The proportion of subjects who progressed in each arm will be summarized. Each component of progression will be summarized descriptively. If a subject who was not on background therapy at randomization initiates treatment with background therapy during the study, the subject will be censored at the time of new background therapy initiation.

Other time-to-event types of endpoints, e.g., time to first acute exacerbation, time to death or lung transplant, nonelective hospitalization (due to respiratory causes and due to all causes), and

CONFIDENTIAL

The information contained herein may not be used, disclosed, or published without the written consent of Biogen MA Inc.

survival rate (death from all causes and death due to respiratory causes) at 26 weeks and 52 weeks will be analyzed similarly.

The number of subjects experiencing an absolute decline of 10% predicted in FVC will be analyzed using a logistic regression model, adjusting for the randomization stratification factor, patient age, and baseline FVC.

Other pulmonary function endpoints and the 6MWT at 52 weeks will be analyzed similarly to the primary endpoint. For other visits, an analysis of covariance model adjusting the randomization stratification factor, age, and FVC at Baseline will be used to compare the treatment groups. The cumulative distribution of subjects by change in absolute and percent predicted FVC from Baseline to Week 52 will be presented in graph form.

Details of the analyses, including the handling of missing data, will be described in a SAP.

[REDACTED]

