1.2 TABLES, FIGURES AND LISTINGS

A detailed description of the planned Tables, Figures, and Listings (TFLs) to be presented in the clinical study report (CSR) is provided in the accompanying TFLs shell document. When the SAP and TFL shells are agreed upon and finalized, they will serve as the template for this study's CSR.

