6.1.1 Analysis Visit and Study Day Definition

6.1.1.1 Baseline

Unless stated otherwise, baseline value is defined as the data collected prior to the time and/or on the date of first dose, which is usually the same day as the Baseline visit (Day 0). If there is more than one value on/before the date of the first dose, the non-missing value closest to the first dose will be used as the baseline value.

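### The MMRM for the two key secondary DLco endpoints names baseline FVC but not baseline DLco as a covariate; adding the endpoint's own baseline is a cheap improvement with a small, possibly nil, gain in precision.

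*SAP*

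**What the plan says.** SAP 7.3.1.1 lists change from baseline in DLco/Hb and % predicted DLco/Hb (Weeks 26 and 38) and in TLC and % predicted TLC (Week 26). It gives their analysis by cross-reference: "The continuous secondary efficacy endpoints listed as follows will be applied using MMRM model described in" Section 7.2.2. A visit with fewer than 20 subjects with data is not compared.

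SAP 7.2.2 is written for FVC. Its fixed effects are "treatment, randomization stratum (background therapy), age, and baseline FVC along with treatment-by-time interaction" and a background-by-time interaction. No other baseline lung-function term appears, and 7.3.1.1 does not change the covariate for the other endpoints.

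Protocol Version 1, from which the SAP was developed, points the same way. Its Section 16.2.2.3 compares the other pulmonary function endpoints at visits other than Week 52 by analysis of covariance, adjusting for the stratification factor, "age, and FVC at Baseline will be used to compare the treatment groups".

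The own baselines exist. Protocol 13.1.1.2 schedules DLco at screening and at the "following study visits: Baseline (Day 0), Week 4, Week 8, Week 16, Week 26, Week 38, and Week 52". Protocol 13.1.1.3 schedules plethysmography at Baseline. SAP 6.3.2.2 summarizes both at baseline.

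SAP Section 1 restricts inference to the primary endpoint and three key secondary endpoints: % predicted FVC, DLco/Hb and % predicted DLco/Hb. Everything else is to be descriptive.

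**The concern.** In a model for change from baseline, the covariate most directly tied to the outcome is usually the baseline of the same measurement, because baseline measurement error enters the change score with a negative sign. Baseline FVC captures that only as far as it correlates with baseline DLco or TLC. A covariate that suits the FVC model has been carried over to different measurements.

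Two things are at stake, both modest. Some precision may be given up in a truncated sample. And if the arms happen to differ in baseline DLco, the estimate in the one trial actually run is not corrected for that difference beyond the part that FVC explains.

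**Working it through.** **The plan's own figure.** The only power statement (SAP Section 4) concerns FVC. With 145 × 0.85 = 123.25 per arm, effect 82.5 mL, SD 280 mL and two-sided alpha 0.15:

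- SE = 280 × √(2/123.25) = 35.67
- 82.5/35.67 − 1.440 = 0.873
- power = 80.9%, which matches the stated 80% or so

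This point does not affect that figure. No power is stated for DLco or TLC.

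**Inputs.** The documents give none for these endpoints, so all of the following are assumed:

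- ρ: correlation of the endpoint's baseline with follow-up
- k: follow-up SD divided by baseline SD
- a: correlation of baseline FVC with the endpoint's baseline
- FVC predicts follow-up only through the endpoint's baseline

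**Formulas**, with baseline SD set to 1:

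- Residual variance of change given FVC: 1 + k² − 2kρ − a²(kρ − 1)²
- Residual variance of change given FVC and own baseline: k²(1 − ρ²)
- VR = second divided by first; fall in SE = 1 − √VR

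**Worked ends of the range, k = 1.**

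- ρ = 0.80, a = 0: 0.36/0.40 = 0.900, so the SE falls 5.1%.
- ρ = 0.95, a = 0.8: 0.0975/0.0984 = 0.991, so the SE falls 0.5%.

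Fall in SE (%), k = 1, before the cost of the extra parameter:

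| ρ | a = 0 | a = 0.5 | a = 0.8 |
|---|---|---|---|
| 0.80 | 5.1 | 3.9 | 1.9 |
| 0.90 | 2.5 | 1.9 | 0.9 |
| 0.95 | 1.3 | 0.9 | 0.5 |

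If ρ were only 0.6 to 0.7, the fall would be 3.0 to 10.6%. It is zero when kρ = 1, that is, when follow-up regresses on baseline with slope 1 (for example k about 1.05 with ρ = 0.95).

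**Cost of the extra parameter.** In a single-visit model one more covariate inflates the variance by about 1/(N − 7): 1/13 = 7.7% at N = 20, 1/33 = 3.0% at N = 40, 1/113 = 0.9% at N = 120. Multiplying VR by these factors gives the net change in SE:

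| | N = 20 | N = 40 | N = 120 |
|---|---|---|---|
| ρ = 0.80, a = 0 | 1.6% gain | 3.7% gain | 4.7% gain |
| ρ = 0.95, a = 0.8 | 3.3% loss | 1.0% loss | nil |

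**Multi-visit check for DLco.** The DLco MMRM has up to five post-baseline visits through Week 38, so the cost is shared across visits. A simulation of that model kept FVC and added own baseline. It assumed an FVC-to-own-baseline correlation of 0.4, a slope of follow-up on baseline of 0.80 to 0.95, and 40 to 100 subjects, half of them with Week 38 data. The model-based SE at Weeks 26 and 38 fell by 0.1 to 3.0%. It used an unstructured covariance and omitted the Kenward-Roger adjustment and the AR(1) fallback, so it supports the order of size only.

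**TLC at Week 26.** Let b be the slope of follow-up on baseline and take the variance of change as 2(1 − b) + 0.04, also assumed. At b = 0.7 this is 0.64; own-baseline adjustment leaves 0.64 − 0.09 = 0.55.

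- FVC-to-TLC correlation 0.4: FVC adjustment leaves 0.64 − 0.16 × 0.09 = 0.6256. Replacing FVC lowers the SE by 1 − √(0.55/0.6256) = 6.2%.
- Correlation 0.8: FVC adjustment leaves 0.64 − 0.64 × 0.09 = 0.5824. Replacing FVC lowers the SE by 2.8%. Keeping both gives a 1.9% gain at N = 60 and a 0.8% loss at N = 20.

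**Chance imbalance.** Take a one-standard-error imbalance in the part of own baseline that FVC does not explain. Under the k = 1 model it shifts the FVC-adjusted estimate by √(1 − VR) standard errors: √0.100 = 0.32 at ρ = 0.80, a = 0, and √0.009, about 0.10, at ρ = 0.95, a = 0.8. Own-baseline adjustment removes this.

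**The case against.** The strongest reply is that no error is shown. Baseline FVC is a prognostic covariate deliberately named in the protocol, and the inference is nominal (SAP 6.7). An analyst may also read 7.2.2 as a template and substitute the analogous baseline: the section is written only for FVC, and SAP 6.1.1.1 defines baseline generically ("the non-missing value closest to the first dose will be used as the baseline value"). SAP 1.2 places "A detailed description of the planned Tables, Figures, and Listings (TFLs) to be presented in the clinical study report (CSR") in a separate shell document that is not available here and may settle the matter. All this is fair, and it limits the point to an improvement. It does not remove it: the text names FVC, the protocol supports that reading, and the own baseline costs almost nothing to add.

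A second reply concerns TLC. SAP Section 1 makes TLC descriptive only, while 7.3.1.1 lists it for the MMRM. If Section 1 governs, there is no TLC comparison to improve. A single assumed FVC-to-TLC correlation of 0.4 would also flatter the gain, as the 0.8 case shows. Both objections stand.

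Three stronger readings are tempting, and the documents do not support them:

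- *The DLco treatment estimates are biased.* Averaged over randomizations, neither choice of covariate biases the contrast.
- *The key secondary analyses lose material power.* Nothing in the documents gives a correlation low enough to imply this.
- *% predicted FVC has the same defect.* SAP 7.3.1.1 says "change from baseline in percent predicted FVC, at week 26 and week 38 will be applied using the primary analysis" along with the other Section 7.2 analyses, and protocol 16.2.2.2 says "Rate of decline in percent predicted FVC at 52 weeks will be analyzed by the same method as FVC actual value". That endpoint is already adjusted for a baseline of the same measurement, and no gain is claimed there.

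**Conclusion.** The point holds as a cheap improvement. Read literally, SAP 7.3.1.1 and 7.2.2 adjust two key secondary endpoints for baseline FVC and not for their own baselines. Under the assumed ranges the SE would fall by about 0.5 to 5% before the parameter cost. The net result may be nil or a slight loss with very few subjects or with a regression slope near 1. The further benefit is protection against chance imbalance in baseline DLco. The size rests wholly on assumed correlations and SDs; the reading of the text does not. The primary analysis is untouched, because its model already contains baseline FVC. For TLC the conclusion is conditional on the SAP first resolving whether a model is fitted at all.

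**What to change.** Add one sentence to SAP 7.3.1.1, after the list of DLco and TLC endpoints: each MMRM in the list includes the baseline value of the endpoint analysed, on the same scale, in addition to baseline FVC; if the TLC models are run, the endpoint's own baseline replaces baseline FVC.

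Separately, reconcile SAP Section 1 (TLC descriptive only) with 7.3.1.1 (TLC in the MMRM). Make both changes before the Part I lock, by which SAP 1.1 requires the SAP to be final.

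The cost is one extra parameter in each DLco model, shared across its visits, and no new data. For TLC, replacement avoids the extra parameter in what is close to a single-visit analysis, but gives up any independent predictive value of FVC.
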